5.3. Medical Record Review for Index Hospitalization

Delirium etiology during index hospitalization will be determined using the **Delirium Etiology Checklist (Appendix T)** which classifies delirium etiologies into 13 categories.⁶⁰ Using medical record review, delirium etiology will be independently determined by two physician reviewers who have expertise in delirium; any disagreements will be adjudicated by a third physician reviewer. If the inter-rater reliability between the emergency physician and physician reviewers is good (kappa > 0.60), then the emergency physician's delirium etiology rating will be used for the LCA. For the purpose of our analysis, delirium etiologies will be collapsed into the following categories based upon our preliminary data: (1) CNS, (2) metabolic, (3) systemic infection, and (4) other. The physician reviewers will also record what treatments were provided and determine if the delirium etiologies were treated adequately.

Additional data will be collected from the medical record and is summarized in **Table 5**.

	Outcome Variable	Description	Source	Length
Primary Outcome	Repeatable Battery for the Assessment of Neuropsychological Status (RBANS, Appendix E) ⁶⁷	A neuropsychological battery for global cognition which evaluates immediate and delayed memory, attention, visuospatial construction, and language. It has been validated in subjects with mild cognitive impairment, moderate to severe traumatic brain injuries, vascular dementias, and Alzheimer's disease. ⁶⁷⁻⁷¹ Scores range from 40 to 160, and the population mean (SD) is 100 (15).	Patient	30 mins
Secondary Outcomes	Delis-Kaplan Executive Function System (D-KEFS) Proverbs subscale (conceptual flexibility, Appendix F), the DKEFS Color Word Interference (inhibition, Appendix G), and DKEFS Verbal Fluency Category Switching subscale (monitoring, Appendix H) ⁷²	This neuropsychological battery will be used to quantify executive function. It assesses conceptual flexibility, inhibition, and monitoring which are the cornerstones of executive function. ⁷² An executive function composite score will be calculated from these three DKEFS subscales.	Patient	10 mins
	Older American Resources and Services Activities of Daily Living Scale (OARS ADL, Appendix I) ⁵⁸	It is based upon 7 basic and 7 instrumental activities of daily living. Scores range from 0 (completely dependent) to 28 (completely independent).	Patient or informant	5 mins
	EQ-5D-5L (Appendix J) ⁷³⁻⁷⁵	EQ-5D-5L characterizes quality of life and contains 5-dimensions ("5D") related to everyday living: mobility, self-care, usual activities, pain/discomfort, and anxiety/depression. The EQ-5D-5L asks patients to grade their current global health status from 0 (worst health you can imagine) to 100 (best health you can imagine).	Patient	5 mins

	Rehospitalization and nursing home placement	While attempting to contact the subject or surrogate, we will determine if the patient was rehospitalized or placed in a nursing home.	Patient or informant	1 min
	Death	To be ascertained via medical review, subject or surrogate contact, obituary searches, and National Death Index.	Informant, electronic health record	1 min

Table 6. Four-month outcome variables to be collected.

5.4. Outcome Variables for Aim #1 (randomized control trial)

Four months (3 to 7 months) after randomization, subjects will return to the local site for outcome ascertainment. For those who are unable to travel, a member of the neuropsychological team will travel to the patient's home. The primary and secondary outcome variables to be collected at 4-months (range 3 to 7 months) are listed in **Table 4**. We will also investigate the effect of cognitive training on **index hospital outcomes** as part of our secondary analyses. We will collect delirium duration using the modified bCAM, and hospital length of stay, ICU length of stay, and post-discharge disposition (e.g., skilled nursing facility) to be collected via medical record review. Based upon the neuropsychological raters' observations, they will also determine the Clinical Frailty Scale (Appendix N). They will also collect the **Mini-Nutritional Assessment (Appendix M)** for covariate adjustment.

5.5. Outcome Variables for Aim #2 (MRI)

Functional magnetic resonance imaging (fMRI) will be performed at 4 (range 3 to 7) months after randomization at the Vanderbilt University Institute of Imaging Science (VUIIS). Because of the 1:2 random allocation, one out of two controls will be randomly selected to participate in the fMRI aim. Patients will be scanned using dual-channel body coil radiofrequency transmission and SENSE-array 32-channel reception with the following protocol:

- Functional MRI.* Whole-brain gradient echo blood oxygenation level-dependent (BOLD) fMRI will be performed using a single-shot EPI multiband (factor=2.0) readout with spatial resolution=2x2x2 mm³ and TR/TE=1000/35 ms. The acquisition will be performed during a face/scene delayed matching task⁷⁶ during fMRI acquisition using standard seed-based as well as minimum spanning tree (MST) analysis. This face/scene delayed matching task evaluates selective attention and working memory, and is designed to target medial temporal lobe and frontal and parietal cortices.⁷⁷
- Perfusion imaging.* We will perform pseudo-continuous arterial spin labeling (pCASL) to obtain quantitative perfusion maps (ml blood / 100g tissue / min). Here, we will apply Hanning-windowed block pulse labeling (pulse-train duration=1600 ms) followed by post-labeling delay=1800 ms with TR=4.1s. Labeling will occur 90 mm inferior to the AC/PC line. We will apply a 3D GRASE readout (spatial resolution=3x3x5 mm³; SENSE (Phase)=3; SENSE (Slice)=2; turbo direction=slice) with background suppression. A TR=20s equilibrium magnetization (M_0) image with identical geometry as pCASL but with labeling removed will also be acquired.
- Anatomical.* T_1 -weighted (MPRAGE; spatial resolution=1.0x1.0x1.0 mm³; TR/TE=8.2/3.7 ms), T_2 -weighted FLAIR (spatial resolution=0.9x1.1x3.0 mm³; TR/TI/TE=11000/2800/120 ms), T_2^* -weighted (spatial resolution=0.5x0.5x1mm³; TR/TE₁/ΔTE=31/7.2/6.2 ms), and intracranial and extracranial time-of-flight MR angiography (TOF-MRA; intracranial: spatial resolution=0.5x0.8x1.4 mm³, TR/TE=18.6/3.2 ms; extracranial: spatial resolution=0.9x0.9x3.0 mm³; TR/TE=18.6/3.2 ms).

The brain MRI data will be interpreted by [name] staff at the Vanderbilt University Institute of Imaging Science using the following approaches:

- a. *Functional MRI.* BOLD data will be corrected for motion, baseline drift, and slice-time and will be analyzed using standard seed-based functional connectivity and more novel MST following previously-reported standard procedures in eloquent functional networks known to be affected by delirium.^{78,79} Individual-subject t- and z-statistic connectivity maps will be calculated, along with betweenness centrality and degree (from MST analysis); maps will be warped using FSL FLIRT and FNIRT⁸⁰ to a 2 mm MNI atlas using a T₁-weighted anatomical image as an intermediate template.
- b. *Perfusion imaging.* pCASL data will be corrected for motion and baseline drift, surround-subtracted,⁸¹ and normalized by M_0 to generate a difference magnetization map ($\Delta M/M_0$); these values will subsequently be converted to CBF in absolute units upon application of the flow-modified Bloch equation⁸² and transformed to the standard atlas using identical procedures as outlined for BOLD.
- c. *Anatomical.* Tissue volume will be quantified from the T₁-weighted images using Freesurfer and quantitative metrics of tissue volume in all brain lobes will be recorded.

5.6. Plasma biomarkers of inflammation (IL-6 and CRP), endothelial dysfunction (PAI-1), and BBB injury (S100B) using blood specimens collected at enrollment. Within 1 hour of blood draw, the blood will be centrifuged, processed, and stored in a -80° Celsius freezer. These plasma biomarkers will be batch measured in years 3 and 4 at the [name] Laboratory using Electrochemiluminescent assays (IL-6, CRP, and PAI-1, Meso Scale Discovery; Rockville, MD) and sandwich ELISAs (S100B; Millipore; Billerica, MA). Plasma biomarkers will be measured in blood collected at enrollment and 72 hours. Additional blood may be collected at 120-hours for future analyses, but will be optional; some patients no longer have routine blood draws by 120-hours. Additional blood will be collected at enrollment for future genetic analysis. Urine will also be collected at baseline, 72-hours, and 120-hours for future analyses.

5.7. Database management

This study will use REDCap for data collection, transmission, and storage. REDCap is a secure, web-based application for building and managing online databases. Vanderbilt University Medical Center, with collaboration from a consortium of institutional partners, including the Vanderbilt Institute for Clinical and Translation Research (VICTR) Informatics Core, developed and manages a software toolset and workflow methodology for electronic data collection and management of research and clinical trial data. All study data will be entered via a password-protected, study unique REDCap database website. REDCap servers are housed in a local data center at Vanderbilt University Medical Center, and all web-based information transmission is encrypted. REDCap was developed specifically around HIPAA-Security guidelines and is recommended by both the Vanderbilt University Medical Center Privacy Office and Institutional Review Board. REDCap has been disseminated for use locally at other institutions and currently supports > 140 academic/non-profit consortium partners and 11,000 research end-users (www.projectredcap.org).

Whenever possible, data will be directly entered into electronic case report forms (eCRFs) within REDCap. When paper-based surveys or forms, such as the RBANs, are collected, these forms will be entered or uploaded into REDCap. The paper CRFs will only have the patient's unique identification number and initials. These case report forms will then be stored in a locked cabinet in a secure office space. All paper case report forms will be kept according to Institutional Review Board (IRB) policies.

All research materials will only be accessible by IRB approved research personnel. Principal investigators, co-investigators, study coordinators, Cognitive Intervention Specialist, CTAs, and neuropsychological raters will have access to individually identifiable private information. Such access is necessary for conducting medical record review and follow-up. The rest of the study team (e.g., biostatisticians) will only have access to de-identified data.

5.8. Reimbursement

We will provide \$75 for patients to complete the ED, hospital, and 12-week post-discharge assessments. We will also provide participants financial compensation (\$75) the 4-month follow-up. Patients will receive an additional \$50 if they participate in the brain magnetic resonance imaging (MRI) study. For patients who develop significant functional impairment or are unable to travel (~30% of cohort), the neuropsychologists will go to their homes to conduct the long-term cognitive and secondary outcomes assessments. These patients will be reimbursed \$25.

6.0 Risks

There are several risks associated with this R01:

- 1) Risks associated with the collection of protected health information. Collection of protected health information for research involves a small risk of the loss of patient confidentiality. To minimize this risk, at no time will we reveal subject identities in any manner, whether in presentation, description, or publication of the research for scientific purposes. Most data will be directly entered into a HIPAA compliant REDCap electronic database. These data will be stored on a secure network on Vanderbilt's computer servers. While data will be entered electronically whenever possible, paper-based case report forms may still be used to collect neuropsychological data (e.g., figure drawing and recall). The paper-based case report forms will have the patient's study identification number and initials only; no other patient identifiers will be present. All paper-based case report forms and questionnaires will be stored in a locked cabinet in office space only accessible to the study team. All case report forms will be kept for 3 years as per Vanderbilt's IRB policy; afterward, all paper documents will be shredded.
- 2) Fatigue, frustration, and distress. Subjects will undergo cognitive training, cognitive rehabilitation, and a neuropsychological examination that can take up to 45 minutes to perform. Some of the tasks related to the cognitive intervention and testing are also cognitively demanding. Therefore, there is a small risk that the patient may become fatigued, frustrated, or distressed during the cognitive intervention or assessments. In these cases, we will immediately stop the assessment or tasks, and allow the patient to rest. Afterward, we will ask the patient and their families if we can continue with the study assessments or cognitive training or rehabilitation session, or if we should come back later in the day or the next day. Occasionally, patients and their families may get visibly frustrated and distressed if the patient is unable to perform the cognitive tasks. We will reassure them that these tasks can be difficult to perform and that such difficulties are common. If the patient or his / her family continues to be distressed after this reassurance, we will skip that task or stop the assessment altogether.
- 3) Phlebotomy. All participants will have blood drawn for research purposes. As almost all participants will have intravenous lines placed for clinical purposes, the risk of blood draws is essentially nil, as blood can be easily obtained from these lines. In the rare case an intravenous line is not present, the risks of drawing blood are uncommon and include bleeding and bruising. Commonly, drawing blood is painful, and rarely, drawing blood can lead to infections at the site of the blood draw. To minimize this risk, we will prep the phlebotomy site with chlorhexidine (antiseptic fluid) and use the smallest gauge needle possible. We will also minimize the number of attempts.

4) Distress secondary to fMRI. A subset of 50 patients will undergo fMRI examination which can take 45 minutes to perform. There is a small risk of distress secondary to claustrophobia. To minimize this risk, patients will have an opportunity to opt-out of the fMRI portion, especially if they are claustrophobic. If the subject is in the MRI scanner and cannot tolerate it, then the MRI will be stopped immediately. We will ask the subject if they will be able to proceed with the MRI. If they are unable to continue, we will withdraw the patient from this portion of the study.

7.0 Safety Monitoring, Reporting of Adverse Events or Unanticipated Problems involving Risk to Participants or Others

Because the cognitive training and rehabilitation is a non-pharmacologic intervention, the intervention poses minimal risk to the patient. Therefore, we will not have a formal DSMB. However, [name] (Indiana University) will independently serve as the data and safety monitor; he is not part of the study team and will not participate in any study or publication activities related to this R01. He will also review all data relevant to safety (including all clinical outcomes, SAEs, and unexpected AEs) in once a year during prospective enrollment. He will have access to unblinded data in order minimize potential for bias while maintaining appropriate safety monitoring. After this safety review, [name] will provide a written report to the PIs. The PIs will provide this to the Vanderbilt IRB and the National Institute on Aging.

8.0 Study Withdrawal/Discontinuation

If patient or caregiver declines participation at the outset or does not meet inclusion criteria, they will not be included in the study. If patients wish to discontinue taking part in the study, they will be instructed to contact principal investigator or the research staff and let them know that they wish to withdraw. At that time, no further data will be collected on the patient. All health data previously collected before they withdraw their consent will still be used for reporting and research quality.

9.0 Statistical Considerations

$$\text{Aim #1 Formula} \quad \text{4-month global cognition} = \boxed{\text{Cognitive training / rehabilitation intervention}} + \text{premorbid cognition + premorbid intelligence + covariates + pre-existing ADRD*cognitive intervention}$$

9.1. Data analysis for Aim #1 (cognitive training/intervention RCT and 4-month global cognition): The primary analysis for Aim #1 will be an intention-to-treat comparison of 4-month global cognition between those who receive and not receive the cognitive training and rehabilitation intervention. Though randomization theoretically accounts for group imbalances and possible confounding, adjusting for strong risk factors for outcomes reduces measurement error, which may increase statistical power.⁸³ Therefore, we will use multivariable linear regression using the formula below and adjust for pre-illness cognition and other covariates listed in **Table C8.1.a**:

Covariates that occurred after randomization (e.g., interventions provided during hospitalization) will not be adjusted for because they may potentially be affected by the cognitive intervention and be on the causal pathway. We will also determine if pre-existing ADRD modifies any association between cognitive intervention and 4-month outcomes by incorporating a two-factor interaction (pre-illness ADRD*cognitive intervention) into the model. In the event of significant missing covariate data, multiple imputation will be used.⁸⁴⁻⁸⁶ After the initial analysis has been completed, we will also evaluate if there is any **effect modification** of baseline severity of illness (APS), race, sex, and initial delirium psychomotor, arousal, severity, etiology, and pathophysiological subtypes. To determine if using a delirium assessment affects our conclusions, we will also perform a **sensitivity analysis** where the multivariable linear

regression model is re-run in a subset of patients who are positive for other delirium assessments (CAM, 3D-CAM, 4AT).⁴⁴⁻⁴⁷

Secondary analyses will also be performed. We will perform a per protocol analyses; for the multivariable linear regression model, the dose of the interventions (total duration of cognitive training and total duration of cognitive rehabilitation) will be the primary independent variables instead of treatment assignment (cognitive training/rehabilitation versus placebo). We will determine if early cognitive training and rehabilitation are associated with our 4-month secondary endpoints such as the individual RBANS cognitive domains (immediate and delayed memory, attention, language, and visuospatial construction), executive function, functional status, rehospitalization, nursing home placement, and death. We will also determine if early cognitive training reduces delirium duration, hospital length of stay, and discharge to a post-acute care facility. We will also explore if there are specific interventions that potentiate the cognitive intervention's effect such as time-to-cognitive training, discharge to a post-acute care facility, and physical activity during cognitive rehabilitation (mean Life Space questionnaire scores). We will explore if these factors modify the association between the cognitive intervention and 4-month global cognition.

9.2. Data analysis for Aim #2 (fMRI). To test if frontoparietal network connectivity, as characterized by BOLD fMRI, improves with cognitive training/rehabilitation compared with controls, we will apply the co-registered z-statistic maps in a mixed effects model to evaluate regions that differ in activation between the two groups, after separately modeling age, sex, and pre-illness QDRS. Group-level z-statistics and corrected p-values will be reported. As a supplementary analysis, we will also explore whether (i) regional tissue volumes at the imaging MRI time point vary between groups and (ii) cortical perfusion quantified from pCASL varies between groups. For these comparisons, a Wilcoxon rank-sum test or Student's t-test will be applied. With a sample size of 50 (25 per group), we will have sufficient power to detect a 30% improvement in frontoparietal cortex network connectivity with 80% power and a two-sided alpha of 0.05.

9.3. Data Analysis for Aim #3 (identify novel delirium phenotypes using LCA): Aim #3 will use LCA to identify hidden groups based on the observed delirium subtypes

	df
Primary Independent	
Cognitive intervention	1
Pre-illness Cognition / Intelligence	
Pre-illness ADRD	1
Pre-illness QDRS	1
Propositional density	1
Other Baseline Covariates	
Sex	1
Race	1
Education	1
Pre-illness function (OARS ADL)	1
Severity of illness (APS)	1
Comorbidity Burden	1
Interactions (Maximum)	
ADRD* Cognitive intervention	1
Total Degrees of Freedom (df)	11

Table C8.1.a. Covariates and interaction terms for multivariable linear regression.

[figure not shown]

Figure C8.3.a. Three hypothetical latent classes or phenotypes for delirium.

(arousal, psychomotor, severity, etiology, and pathophysiology) and separate them into mutually exclusive classes. This technique can be used to obtain phenotypes of delirium and determine if these novel phenotypes are associated with 4-month global cognition. Based upon our preliminary study (**Section C1.5**), pre-existing ADRD may strongly influence these delirium latent classes and will be considered for the LCA. The “best” number of latent classes is usually determined a priori by the researcher and we hypothesize that the cohort will be represented by three delirium phenotypes (**Figure C8.3.a**): no or mild, moderate, or severe 4-month cognitive impairment. The sensitivity of this hypothesis, model fit, and identification of the correct number of unique delirium phenotypes will be evaluated by comparing the models assuming different number of classes using the bootstrapped likelihood ratio test, which is a parametric bootstrap method that uses bootstrap samples to estimate the distribution of the log likelihood difference test statistic.⁸⁷

Once the latent classes have been identified, we will explore if the delirium phenotypes identified by LCA modify the association between the cognitive training and rehabilitation intervention and 4-month global cognition using multivariable linear regression as described in **Section C8.1a** using the formula below:

$$\text{Aim #3 Formula} \quad \begin{array}{l} \text{4-month global cognition} = \end{array} \quad \begin{array}{l} \text{Cognitive training /} \\ \text{rehabilitation} \\ \text{intervention} \end{array} \quad + \quad \begin{array}{l} \text{Phenotypes identified} \\ \text{by latent class analysis} \end{array} \quad + \quad \begin{array}{l} \text{+ premorbid cognition + premorbid} \\ \text{intelligence + covariates +} \\ \text{cognitive intervention*phenotypes} \end{array}$$

The multivariable linear model for Aim #3 will be adjusted for the covariates listed **Table C8.1.a.**

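### Protocol 9.2 compares 4-month brain volumes and perfusion without the covariates it uses for connectivity, which gives up some precision in an exploratory comparison limited mainly by 25 patients per arm.

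*Protocol*

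**What the plan says.** Protocol 9.2 treats the Aim 2 imaging measures in two ways.

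- **Connectivity.** The z-statistic maps enter a mixed effects model that compares the groups "after separately modeling age, sex, and pre-illness QDRS".
- **Volumes and perfusion.** These are labelled supplementary: "we will also explore whether (i) regional tissue volumes at the imaging MRI time point vary between groups", and the same is asked of pCASL cortical perfusion. The method is: "For these comparisons, a Wilcoxon rank-sum test or Student's t-test will be applied". No covariate is named.

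On the measures, Protocol 5.5 says that Freesurfer is run on the T1-weighted images and that "quantitative metrics of tissue volume in all brain lobes will be recorded". It does not mention intracranial volume or any scaling for head size. Perfusion is normalised by the M0 image and expressed as blood flow per 100 g of tissue per minute. Table 4 of the Protocol places the brain MRI only at the 4-month visit.

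The section's power statement is for 25 patients per group to "detect a 30% improvement in frontoparietal cortex network connectivity with 80% power and a two-sided alpha of 0.05". Nothing comparable is given for volumes or perfusion. The SAP's stated objective is the Aim 1 question only, so it neither repeats nor changes this part of the Protocol.

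**The concern.** With one scan per patient, lifelong differences between people in brain volume or blood flow cannot be removed by a change score. They stay in the error term unless covariates absorb them. Three candidates (age, sex and pre-illness QDRS) are already collected and already used for connectivity in the same patients. Protocol 9.1 also argues, for Aim 1, that adjusting for strong predictors of outcome may raise power. Section 9.2 gives no reason for dropping them for the two supplementary measures.

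For volumes there is one further candidate, head size, on which the Protocol is silent. What is at stake is the width of the confidence intervals for volume and perfusion. No stated hypothesis of the trial rests on these measures.

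**Working it through.** **Inputs from the documents.** 25 per group (Protocol 9.2); one scan at 4 months, range 3 to 7 (Protocol 5.5); two-sided alpha 0.05 and 80% power, borrowed from the connectivity statement.

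**Inputs assumed.** The documents give no SD for volume or perfusion, so results are in SD units. They give no share of variance explained by the covariates (R²), so R² is set at 0.1, 0.3 and 0.5.

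**1. The plan's own figure.** The 80% power for a 30% improvement in connectivity cannot be reproduced, because no SD is stated. It implies a coefficient of variation of 0.30 / 0.792 = 0.38 (normal approximation) or 0.30 / 0.809 = 0.37 (t-test). Power would be 93% at a coefficient of variation of 0.3, 74% at 0.4 and 55% at 0.5. The figure does not bear on volumes or perfusion.

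**2. Unadjusted comparison as planned.** Detectable difference = (z0.975 + z0.80) × √(2/25) = (1.960 + 0.842) × 0.283 = 0.79 SD.

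- Exact t-test, 48 degrees of freedom: 0.81 SD.
- Wilcoxon, taking its efficiency relative to the t-test as 0.955 under normality: 0.83 SD.

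**3. Adjusted comparison.** With four covariates (age, sex, QDRS, intracranial volume) the error degrees of freedom are 50 − 2 − 4 = 44. At R² = 0 the detectable difference would be 0.810 SD, against 0.809 unadjusted, so the degrees of freedom cost almost nothing. In general:

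Detectable difference = 0.810 × √(1 − R²)

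Equivalent unadjusted n per arm = 25 / (1 − R²)

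| | Detectable difference (SD) | Equivalent n per arm | Power for 0.5 SD | Power for 0.3 SD |
|---|---|---|---|---|
| Unadjusted t-test | 0.81 | 25 | 41% | 18% |
| R² = 0.1 | 0.77 | 27.8 | 45% | 19% |
| R² = 0.3 | 0.68 | 35.7 | 54% | 24% |
| R² = 0.5 | 0.57 | 50 | 69% | 31% |

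With three covariates, as for perfusion, the multiplier is also 0.810 and the detectable differences are the same to two decimals. The R² reached may well differ between the two measures.

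**4. What limits the comparison.** A 0.5 SD difference would need 63 per arm unadjusted, against 25 planned. Even at R² = 0.5, power for 0.3 SD is only 31%. If 20 per arm are scanned instead of 25, the unadjusted detectable difference rises to 0.91 SD. Sample size is the main constraint, and adjustment relieves part of it.

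**The case against.** The strongest reply is that nothing here is wrong. The arms are randomised and the controls for imaging are drawn at random, so a two-sample test is valid. Chance imbalance in sex or dementia stage is already covered by its 5% error rate. The analysis is labelled supplementary, and a simple test is a defensible choice for it. At R² = 0.1 the gain, from 0.81 to 0.77 SD, is trivial. All of this stands, and it is why the point is only a cheap improvement.

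Four stronger readings are tempting, and the documents do not support them.

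- **That the unadjusted comparison is biased.** Scanned patients must survive, have no MRI contraindication and not opt out, so they are a selected group. Nothing in the documents shows that this selection differs by arm.
- **That lack of adjustment is why only large differences can be seen.** The 25 per arm is the main reason, and small effects stay undetectable after the fix.
- **That perfusion lacks head-size scaling.** It is already expressed per mass of tissue.
- **That volumes will be analysed raw.** The Protocol does not say so; scaling is simply unspecified.

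A last objection is that Protocol 9.1 rules out covariates arising after randomisation, and intracranial volume would be measured at 4 months. The stated reason for that rule is that the intervention may affect such variables. Adult head size should not respond to cognitive training, though this is an assumption. Age, sex and pre-illness QDRS do not raise the issue.

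**Conclusion.** The point holds as a loss of precision. For volumes and perfusion, Protocol 9.2 specifies tests that leave out baseline covariates used for connectivity in the same section, and it gives no reason. At 80% power the detectable difference is about 0.81 SD as planned and about 0.77 to 0.57 SD with adjustment. That is a reduction of 5% to 29%, depending wholly on an assumed R² of 0.1 to 0.5. The figures also assume 25 completed scans per arm and roughly normal outcomes.

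Whether intracranial volume is available, and how much it adds, cannot be settled from the documents. The primary outcome, the connectivity analysis and the SAP are unaffected.

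**What to change.** In Protocol 9.2, change the method for the two supplementary measures:

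- **Lobar volumes:** a linear model on arm, age, sex and pre-illness QDRS, adding intracranial volume if the existing T1 segmentation provides it. State whether the recorded volumes are scaled for head size.
- **Cortical perfusion:** a linear model on arm, age, sex and pre-illness QDRS, with no head-size term.
- **Reporting:** the adjusted arm difference with its 95% CI for each measure.
- **Sensitivity analysis:** keep the unadjusted rank-sum or t-test.

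The SAP, dated November 2024, already describes enrolment and treatment in the past tense. The change should therefore be dated, with a note on whether imaging results by arm had been seen.

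The cost is three or four degrees of freedom from 50 scans and slight extra analysis work. No further scan, visit or patient is needed.
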